11.0 Interim Analyses and DSMB

11.1 Interim Analysis

There are no interim analyses planned for this study following Protocol Amendment #1. As this trial is of exploratory nature and no inferential statistics are planned, no adjustment for multiple testing will be done.

11.2 Safety Monitoring Committees

An independent DSMB will be convened to oversee the safety of subjects participating in this trial. The DSMB will perform a comprehensive review of all relevant safety and reactogenicity data before making a decision to pause the trial (i.e., temporary stopping of enrollment and vaccinations) due to a safety signal in consultation with the Sponsor. CureVac's Safety Review Team (SRT) also reviews the AEs reported across the CV-NCOV clinical trials on a weekly basis and the meeting minutes are shared with the DSMB Chair. For more details about the Protocol Amendment #1 and the description of the changes to the trial see sections 6.1 and 6.2.

For the co-morbidities chronic kidney disease, COPD, chronic cardiovascular disease and diabetes mellitus, the first 25 subjects per co-morbidity should include only mild to moderate cases. The iSRC and DSMB Chair will perform an assessment of the safety and reactogenicity data up to at least 1 week after the first dose, prior to proceeding with enrollment of subjects with more severe forms of the co-morbidity as per the Investigator's decision.

Details on the composition, objectives, and responsibilities of the DSMB, and the schedule and conduct of the DSMB meetings will be described in the DSMB Charter.

The DSMB analyses will be described in a separate SAP and TFL shells.

12.0 Statistical Methods

The SAP V1.0 will be prepared and finalized at the latest prior to database lock.

Subjects will be stratified post-hoc by pre-defined co-morbidities (see Section 10.4). Subjects with multiple co-morbidities will contribute to the different corresponding strata.

Data from this trial may be pooled with data from potential follow-up trials.

Due to the exploratory nature of this trial, only descriptive statistics will be used. No confirmatory statistical inference will be performed.

All data collected during this trial will be displayed in data listings, unless otherwise specified. Data listings will be sorted by co-morbidity definitions - chronic kidney disease, chronic obstructive pulmonary disease (COPD), obesity, chronic cardiovascular disease, chronic HIV infection, type 2 diabetes mellitus and post-renal transplantation and subject identifier. Screening failures will be excluded from all listings and tables if not otherwise stated. Listings will include all relevant assigned/derived variables.

Unless otherwise noted, categorical variables will be summarized using counts and percentages. Descriptive statistics (mean, median, standard deviation (SD), Q1, and Q3, minimum and maximum values) for continuous variable will be presented. Mean, median, Q1 and Q3 will be presented to 1 decimal more than original data. SD will be presented with 2 decimals more than original data. Minimum and maximum will match the decimal points in the original data. Maximum number of decimals will be 4, unless otherwise stated.

In general, all data summaries will be presented by (and in the following order):

- Chronic kidney disease,
- Chronic obstructive pulmonary disease (COPD),
- Obesity,
- Chronic cardiovascular disease,
- Chronic HIV infection,
- Type 2 diabetes mellitus,
- Post-renal transplantation and
- Overall

No imputation of missing data other than that described in Section 10.5 will be performed.

All data summaries and tabulations will be prepared using SAS Version 9.4 or higher.

12.1 Subject Disposition

The number and percentage of subjects who completed the 2-dose vaccination regimen, completed trial, and reason for discontinuing further vaccination and trial will be presented with a breakdown of the corresponding reasons for early termination and discontinuation.

The number and percentage of subjects included in each analysis set will be provided. Reasons for exclusion from each analysis set will not be tabulated, but will be listed.

Subjects not fulfilling one or more inclusion criterion or meeting any of the exclusion criteria will be listed only.

12.2 Demographic and Baseline Characteristics

Demographic characteristics to be summarized based on the Safety Analysis Set (SAS) will include gender, ethnicity, race, age at informed consent (years), age by group (18-60 years, ≥ 61 years), height, weight, Body Mass Index (BMI), height (cm), weight (kg), BMI (kg/m^2), childbearing potential. Subjects co-morbidities will be summarized by severity. Data collected related to the primary co-morbidities will be listed.

12.3 Medical History

Medical history will be coded using the Medical Dictionary for Regulatory Activities (MedDRA) Version 23.1 or higher and will be summarized by Primary System Organ Class (SOC) and Preferred Term (PT) for the SAS. Medical history will also be listed.

12.4 Trial Vaccine Exposure

The number and percentage of subjects who received at least one vaccination on day 1 (dose 1), 29 (dose 2), including the reasons for not receiving a dose will be summarized using the SAS. The administrations of CVnCoV will be listed as well.

12.5 Important Protocol Deviations

Per PRA processes, protocol deviations data will be entered into PRA system of record (PSO). The trial team and the Sponsor will conduct ongoing reviews of the deviation data from PSO and the resulting set of evaluable subjects throughout the trial, adjusting the deviation criteria as seems appropriate.

Protocol deviation data will be reviewed prior to formal analysis (e.g. main, final) and important deviations leading to elimination of subjects from analysis sets will be identified. The detailed definitions of important protocol deviations leading to elimination of subjects from analysis sets will be provided in the final signed minutes of the data review meetings prior to each formal analysis.

A summary of important protocol deviation data will be created based on the SAS, displaying the number and percentage of subjects with any important protocol deviations and broken down by type of deviations. Protocol deviation data will also be listed.

12.6 Prior and Concomitant Medications and Vaccinations

Prior and concomitant medications and vaccinations will be coded using World Health Organization Drug Dictionary (WHODDRUG), Version September 2020 Global B3 or higher, and will be summarized based on the SAS.

Concomitant medications/vaccinations will be summarized by Anatomical Therapeutic Chemical (ATC) level 1 and WHODDRUG Preferred Name as the number and percentage of subjects taking at least one medication within each medication group and subgroup.

Prior medications/vaccinations will be summarized by ATC level 1 and WHODDRUG Preferred Name as the number and percentage of subjects taking at least one medication within each medication group and subgroup.

Medications with ATC level 2 code J07 are considered to be vaccinations.

Concomitant medications and vaccinations will be listed as well.

12.7 Analyses

The primary, secondary and exploratory endpoints will be analyzed overall, as well as per underlying comorbidity.

Based on the Protocol Amendment #1, a subset of analyses will be presented. See Section 6.1, 6.2, 6.3, 6.4 and Appendix 4 List of Abbreviated Scope Based on SAP Version 2.0 for additional details. Below all planned analyses according to SAP version 1.0 will be described. Any analysis not performed according to the abbreviated scope will be described.

Any analysis marked with an asterisk * will not be part of the abbreviated scope described in detail in Appendix 4.

12.7.1 Primary Safety Endpoints

Unsolicited AEs, including SAEs, and AESIs and solicited AE integrated to or recorded on the CRF will be coded using MedDRA Version 23.1 or higher, by SOC and PT.

If not stated otherwise, all summaries/counts of unsolicited AEs will exclude solicited AEs.

For outputs presenting occurrence of AEs for a defined period after a dose, the following distinctions are made if not otherwise stated; by any dose, dose 1, and dose 2. Any dose is defined as a subject who received at least one dose of CVnCoV.

The primary and secondary safety endpoints will be analyzed using the safety set.

12.7.1.1 Analysis of Unsolicited AEs and Solicited AEs

An overall summary of unsolicited AEs will be prepared for AEs occurring within 28 days after each dose, within 28 days after any dose, and all reported AEs (including those reported at more than 28 days after any dose).

- Unsolicited AEs
- Related unsolicited AEs
- SAEs (includes solicited AEs)
- Related SAEs (includes solicited AEs)
- Grade 3 (severe) unsolicited AEs
- Grade 3 (severe) related unsolicited AEs
- Intercurrent medical conditions affecting immune response (includes solicited AEs)
- Medically attended AEs (includes solicited AEs)
- Related medically attended AEs (includes solicited AEs)
- AESIs (includes solicited AEs)
- Related AESIs (includes solicited AEs)
- Medically attended AEs (includes solicited AEs)
- Related medically attended AEs (includes solicited AEs)
- AESIs (includes solicited AEs)
- Related AESIs (includes solicited AEs)
- AEs leading to vaccine withdrawal
- AEs leading to withdrawal from trial

The overall summary will also be presented for overall and by sex (female/male)* and for any dose (dose 1 and dose 2) and include AEs for the duration of the trial.

The following summaries of unsolicited AEs by SOC and PT will further be provided, separately for AEs occurring within the first 28 days after each vaccination, within the 28 days after any vaccination, and all reported AEs (including those reported at more than 28 days after any dose) if not otherwise stated:

- Occurrence of unsolicited AEs
- Occurrence of related unsolicited AEs*
- Occurrence of SAEs (includes solicited AEs)*
- Occurrence of related SAEs (includes solicited AEs) *
- Occurrence of unsolicited AEs by maximum severity (mild / moderate / severe)*
- Occurrence of related unsolicited AEs by maximum severity (mild / moderate / severe) *
- Occurrence of SAEs by maximum severity (mild / moderate / severe) (includes solicited AEs)*

- Occurrence of related SAEs by maximum severity (mild / moderate / severe) (includes solicited AEs)*
- Occurrence of AESIs (includes solicited AEs)
- Occurrence of related AESIs (includes solicited AEs)*
- Occurrence of intercurrent medical conditions affecting immune response (includes solicited AEs)*
- Occurrence of medically attended AEs (includes solicited AEs)*
- Occurrence of related medically attended AEs (includes solicited AEs)*
- Occurrence of AEs leading to withdrawal from trial (includes solicited AEs)
- Occurrence of AEs leading to vaccine withdrawal (includes solicited AEs)
- Occurrence of SMQs (Anaphylactic reaction, Convulsions, Embolic and thrombotic events, Hypersensitivity, Immune-mediated/autoimmune disorders, and Liver related investigations, signs and symptoms (Sub-SMQ)) (includes solicited AEs)*

A listing of all SAEs will further be provided by subject, including both unsolicited and solicited AEs.

Solicited AEs occurring on the day of vaccination and the following 7 days and unsolicited AEs will be listed together.

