## 5.2 Stopping/Pausing Rules for Safety

### 5.2.1 Individual Subject Stopping Rules

Individual stopping AE rules will be applicable during the entire trial to ensure safe administration of the second dose to subjects vaccinated with the first vaccine dose.

Individual subject stopping rules are met in case any of the following events occur on the day of vaccination or the following 7 days (Days 1-8):

- An allergic/anaphylactic reaction considered as related to the trial vaccine.
- Any SAE considered as related to the trial vaccine.
- Any Grade 3 AE considered as related to the trial vaccine, with the following exceptions:
  - Transient Grade 3 systemic AE (fever, headache, fatigue, chills, myalgia, arthralgia, nausea/vomiting and diarrhea) considered as related to the trial vaccine that resolved within 24 hours to Grade ≤2
  - Transient Grade 3 local AE that resolved within 24 hours to Grade ≤2.

If any of these rules are met, the subject must not receive the second vaccine dose. The subject will be encouraged to continue participation until the end of the trial for safety and immunogenicity assessments.

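### The two withdrawal rows of the overall AE summary lack the tag that brings in solicited AEs, so read literally they need not match the SOC/PT tables of the same two measures

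*SAP*

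**What the plan says.** SAP 12.7.1 gives the general rule: "If not stated otherwise, all summaries/counts of unsolicited AEs will exclude solicited AEs".

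SAP 12.7.1.1 then defines the headline table: "An overall summary of unsolicited AEs will be prepared for AEs occurring within 28 days after each dose", with further versions for any dose and for all reported AEs. Several rows switch the default off, for example "Intercurrent medical conditions affecting immune response (includes solicited AEs". The last two rows, "AEs leading to vaccine withdrawal" and "AEs leading to withdrawal from trial", carry no such tag.

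Later in the same section, the SOC/PT list includes "Occurrence of AEs leading to withdrawal from trial (includes solicited AEs" and "Occurrence of AEs leading to vaccine withdrawal (includes solicited AEs", both tagged.

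All of these items stay in the abbreviated report. None has the asterisk that marks dropped analyses, and SAP Appendix 4 keeps Table 14.3.2.1.1 (overall summary), Table 14.3.2.29.1 (study withdrawal) and Table 14.3.2.30.1 (vaccine withdrawal). None of the three Appendix 4 titles says whether solicited AEs are counted. SAP 6.4 lists AEs leading to study or vaccine withdrawal among the key safety analyses of the abbreviated report.

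**The concern.** The same two measures are specified twice within one SAP section, and only the second specification brings in solicited AEs. A programmer who applies the default as written will produce headline counts that can be lower than those in the SOC/PT tables of the same report, with no footnote to explain why.

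For vaccine withdrawal, the events at issue are ones the plan expects. Protocol 5.2.1 withholds the second dose after certain events on Days 1-8, including "Any Grade 3 AE considered as related to the trial vaccine, with the following exceptions". Days 1-8 are the vaccination day and the following seven days, which is also the solicited collection window. At stake are the internal consistency of the safety tables and the correctness of one headline row. No primary estimate, analysis set or decision rule depends on it.

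**Working it through.** The plan states no count or rate on this point, so the check is a comparison of texts.

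**Step 1. Sort the rows of the overall summary.** The list in SAP 12.7.1.1 has 17 bullets. Four are repeats (the medically attended and AESI rows and their related versions), which leaves 17 - 4 = 13 distinct rows:

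- 4 are labelled unsolicited (any, related, Grade 3, related Grade 3).
- 7 are tagged as including solicited AEs (SAEs, related SAEs, intercurrent conditions, medically attended, related medically attended, AESIs, related AESIs).
- 2 have neither label: the withdrawal rows. 4 + 7 + 2 = 13.

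**Step 2. Apply the default to each place where the measures appear.**

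| Output | Measure | Tagged? | Solicited AEs counted under the default? |
|---|---|---|---|
| Overall summary, Table 14.3.2.1.1 | Vaccine withdrawal | No | No |
| Overall summary, Table 14.3.2.1.1 | Trial withdrawal | No | No |
| SOC/PT, Table 14.3.2.30.1 | Vaccine withdrawal | Yes | Yes |
| SOC/PT, Table 14.3.2.29.1 | Trial withdrawal | Yes | Yes |

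**Step 3. Express the difference.** For either measure and the same reporting period, let S be the subjects with at least one solicited AE leading to withdrawal and U those with at least one unsolicited one. The SOC/PT table counts subjects in S or U. The headline row counts U only. The difference is the number in S but not in U, that is, subjects whose withdrawal AEs are all solicited. It cannot be negative, so the headline row can only be equal or lower. If all 129 enrolled subjects (SAP 6.3) were in the Safety Analysis Set, each such subject would shift the overall percentage by 1/129 = 0.8 percentage points.

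**Step 4. Check that S can be non-empty for vaccine withdrawal.** Take a hypothetical subject with a non-serious Grade 3 local reaction after dose 1 that does not fall under a transient-event exception. Solicited local AEs are related by definition (SAP 10.7.2), so the Protocol 5.2.1 rule is met and dose 2 is not given. The subject counts in Table 14.3.2.30.1 but not in the headline vaccine-withdrawal row. If the reaction was also not medically attended, not an AESI and not an intercurrent condition, it enters no row of the overall summary. (Protocol 5.2.1 excepts both systemic and local transient Grade 3 events, whereas SAP 8.2.1 lists only the systemic exception. Those passages need reconciling, but this point stands under either.)

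**Step 5. Check the same for trial withdrawal.** The stopping rules give no comparable route, because a subject who meets one is encouraged to stay in follow-up. The two specifications still differ for this row, but the plan names no mechanism that would make the gap likely.

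**Step 6. Check the neighbouring outputs.** Protocol 8.1 records vaccine discontinuation under an AE category that expressly covers expected vaccine reactions. SAP 12.1 tabulates reasons for discontinuing, and SAP 12.4 reasons for not receiving a dose. The headline row could therefore fall short of the disposition and exposure tables too.

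**The case against.** The strongest reply is that no sentence excludes solicited AEs from the withdrawal rows. The rows that are meant to be unsolicited-only say so, while these two say only AEs. The heading of SAP 12.7.1.1 covers both kinds of event, and the Appendix 4 title of Table 14.3.2.1.1 refers to adverse events in general. The repeated rows point to hurried drafting, and the table shells, which SAP 10.0 places in a separate document, may already settle the scope. This stands in part: the exclusion follows from a default plus a missing tag and is probably unintended. But seven other rows in the same list needed the tag to bring solicited AEs in, so a literal reader has good reason to treat its absence as meaningful.

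The second reply is that nothing is hidden, and this stands in full. The abbreviated scope keeps both SOC/PT withdrawal tables, disposition (Table 14.1.1.3), exposure (Table 14.3.1.1), the listing of product discontinuations (16.2.1.2), the solicited-AE tables by maximum grade (14.3.2.2.1 to 14.3.2.4.1) and a figure of Grade 3 solicited events (14.3.1.1).

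A reader might go further and infer that the omitted events are the main cause of lost second doses, so that the report would make tolerability look better than it was. The documents do not support that. Related SAEs and related allergic or anaphylactic reactions also bar dose 2, transient Grade 3 events are excepted, no split between causes is given, and reactogenicity has its own tables.

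**Conclusion.** The inconsistency is real on the current text and minor. Under the SAP 12.7.1 default, the two headline withdrawal rows leave out solicited AEs while the SOC/PT tables of the same measures include them, so the counts can disagree within one report. For vaccine withdrawal the plan itself supplies a route to disagreement, through non-serious related Grade 3 solicited reactions that bar dose 2. For trial withdrawal there is only the mismatch in wording.

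The size is the number of subjects whose withdrawal AEs are all solicited, and the documents do not give it. A reader might try to estimate it from the Grade 3 adverse-reaction rates in the sample-size section: 129 x 0.05 x 0.10 = 0.6 up to 129 x 0.20 x 0.30 = 7.7 subjects, taking rates of 5-20% and assuming that 10-30% of reactions fall outside the transient exceptions. That range should not be relied on. The rates are hypothetical points on a 5-35% grid (SAP Table 4), they cover related unsolicited Grade 3 AEs as well, they are not limited to dose 1, and the 10-30% share has no source in the documents.

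The conclusion assumes that the default applies to rows labelled simply as AEs inside a summary of unsolicited AEs. If the shells define those rows as all AEs, the counts will agree and only the SAP wording needs correcting.

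**What to change.** In the overall-summary list of SAP 12.7.1.1, add the tag *(includes solicited AEs)* to the vaccine-withdrawal and trial-withdrawal rows, and make the same change in the shell for Table 14.3.2.1.1. Require that table to reconcile, at subject level and for the same reporting period, with Tables 14.3.2.29.1 and 14.3.2.30.1. Any remaining difference from the disposition or exposure reasons should be explained in a footnote. Splitting each row into solicited and unsolicited would also work.

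The cost is two SAP bullets, one table shell and a programming check. No new data are needed. The headline withdrawal counts may rise.

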12.7.1.2 Analysis of Solicited AEs

The following summaries of solicited AEs within 7 days after each trial vaccination and within 7 days after any trial vaccination will be provided. If not stated otherwise the maximum grade will be presented (grade 0 to grade 3).

- Summary of solicited AEs, local AEs and systemic AEs, overall and by maximum grade
- Summary of local AEs, overall and by maximum grade
- Summary of systemic AEs, overall and by maximum grade (occurrence of systemic AEs will also be presented from day -7 until day -1)*
- Summary of related systemic AEs, overall and by maximum grade*
- Duration (days) of solicited AEs, overall and for Grade 3 events
- Duration (days) of local AEs, overall and for Grade 3 events*
- Duration (days) of systemic AEs, overall and for Grade 3 events*
- Duration (days) of related systemic AEs, overall and for Grade 3 events*
- Daily summary of local AEs (only for each dose)*
- Daily summary of systemic AEs (only for each dose)*
- Daily summary of related systemic AEs (only for each dose)*
- Summary of time of onset (Day) for grade 3 solicited AEs, any solicited AEs, local, systemic AEs, and related systemic AEs*
- Time of onset (Day) of local AEs*
- Time of onset (Day) of systemic AEs*
- Time of onset (Day) of related systemic AEs*
- Individual grade 3 solicited local and systemic adverse events will be presented in a figure.*

In addition, number and percentage of subjects with solicited Grade 3 adverse reaction(s) or SAEs considered as related to the trial vaccine according to the Investigator with the 95% credibility interval based on the Beta (0.5, 1.5) prior distribution will be calculated and summarized. This analysis is not part of the abbreviated scope.

Solicited AEs occurring on the day of vaccination and the following 7 days will be listed separately as well.

